### 12.1.4 Urinalysis

Urine samples for determination of urinalysis parameters will be taken at the times given in the Study Plan (Table 2 and Table 3). If deemed necessary, based on a clinically significant positive test, microscopic examination of urine will be performed.

### 12.1.5 Drugs of Abuse

Urine will be tested for the drugs of abuse as described in the Study Plan (Table 2 and Table 3). If a subject fails the drug abuse screen, they will be excluded from the study. A repeat drug

screen can only be done where methodological reasons are believed to have led to a false positive. Borderline positive results, unless covered by the preceding condition, are to be considered as positive and the subject excluded from the study. If subjects are found to be positive due to medication e.g. flu/cold remedies, they may undergo a repeat drug screen if they are still within the screening window. The results from the tests will not be entered into the database.

### **12.1.6 Alcohol Breath Test**

An alcohol breath test will be done using an alcometer as described in the Study Plan (Table 2 and Table 3). The results from this test will not be entered into the clinical study database. If a subject tests positive to the test they will be excluded from the study.

## **12.2 Vital Signs**

### **12.2.1 Blood Pressure, Heart Rate and Tympanic Temperature**

Blood pressure and heart rate will be measured in supine position after the subject has rested comfortably for at least 5 minutes and in standing position after the subject has stood for 1 minute, using automated Criticon Dynamap® monitors. In Part A at H0 and in Part B at H0 and H8 vital signs will only be assessed in supine position, in order to prevent volunteers from standing up and lying down during infusions. Vital signs (blood pressure and heart rate) will be measured at the time points as detailed in the Study Plan (Table 2 and Table 3). Temperature will be measured using tympanic thermometers.

## **12.3 Electrocardiographic (ECG) Measurements**

### **12.3.1 Recording of 12-lead ECGs**

12-lead ECGs will be recorded at the time-points described in Study Plan (Table 2 and Table 3) using a GE Marquette MAC1200® /MAC1200ST® recorder connected via a fixed network connection to the MUSE® Cardiology Information System (MUSE). ECGs recorded during screening will be stored electronically on the MUSE information system. Only ECG recorded electronically will be valid ECG for any purpose other than safety assessment. ECG printouts may be filed in the subject's CRF for medical safety reviews.

Each ECG recorder will be set up to the required technical specifications and containing the information required to identify the records. Each ECG recording will be clearly identified (Subject ID, visit date, and the actual times of ECG recordings).

12-lead ECG recordings will be made after the subjects have been resting in a supine position for at least 10 minutes. The subjects will avoid postural changes during the ECG recordings and clinical staff will ensure that subjects are awake during the ECG recording.

At each time point, the ECG will be recorded in triplicate, to reduce variance and improve the precision of measurement. The triplicates will be performed at approximately 1-minute intervals. Each ECG recording (trace) will last 10 seconds. Repeat ECG will be performed until at least three 10-second ECG records per scheduled time-point meet the quality criteria set out in the SOM and the applicable SOP so to enable reading and analysing at least 5 complexes per derivation.

All recorded ECG will be reviewed by a Research Physician and the review be documented in the CRF. With regards to the clinical assessment of QTc interval, QTcB will be assessed as this is automatically calculated by the equipment. If there is any indication of potential significant QTcB prolongation, QTcF will also be calculated and assessed by a Research Physician. If a subject shows an abnormal ECG, additional safety recordings (including the use of 5 or 12 lead Holter equipment) may be made and the abnormality be followed to resolution if required. Further details will be included in the SOM.

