### 8.2.2 Data Requirements

After each cohort the SRC will assess the minimum safety, tolerability and PK data required prior to dose escalation/progression (refer to dose escalation/progression section [8.2.4](#)). Prior to each SRC meeting, an interim safety report will be prepared for that group/cohort presenting the relevant safety and tolerability data. These will be signed by the PI and/or delegate. PK data will be provided separately by the analytical laboratory. As the initial data review will be blinded, there will be no link between the safety data and the PK data.

The following data will be required:

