#### Safety:

- AEs
- Vital sign variables (temperature, blood pressure, heart rate)
- ECGs variables (12-lead ECG, telemetry and Holter)
- Clinical laboratory variables (haematology, coagulation, biochemistry, urinalysis)

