### 8.2.3 SRC Meeting

The SRC will determine dose escalations/progression according to the Clinical Study Protocol (CSP), anticipated doses, adaptive features and group toxicity rules. The decision will be signed by one of the Sponsor's representatives and by the PI or delegate. For logistical reasons, the signature of the Sponsor or Investigator may be communicated via email.

Initially the data will be reviewed blinded, but if the SRC consider it necessary due to a safety concern, either individual subjects or the entire cohort may be unblinded to enable their decision-making. Before breaking the code, the potential decisions and actions should be determined and documented.

The decision of the SRC on the next dose will be taken in consensus between the members of the SRC. If consensus cannot be reached, then the most cautious approach will proceed. The decisions and decision-making of the SRC on the next dose level will be documented and provided to the PI and Pharmacist prior to the next scheduled dosing day.

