**Table 5. Individual Toxicity Rules.**

Individual toxicity rules		
Grade	Severity/Seriousness	Action
I	Mild	No action required
II	Moderate	IMP administration may be continued, amended, temporarily suspended or discontinued in accordance with Investigator's clinical judgement and relevant algorithms for the treatment of toxicities
III	Severe, not serious	IMP administration will be discontinued for the subject
	Severe, serious	IMP administration will be discontinued for the subject
IV	Life-threatening	IMP administration will be discontinued for the subject
V	Fatal	Not Applicable

Standard toxicity grading according to the National Cancer Institute Common Terminology Criteria (NCI CTC) for AEs (NCI CTCAE, version 4.0) will be used to grade the AEs for the purpose of applying the toxicity rules. This is owing to the fact that these are the only standardised set of comprehensive criteria available and have proven useful in healthy volunteer and patient Phase 1 studies. Local laboratory normal values will be applied. Abnormal laboratory and other tests and measurements will be repeated whenever feasible and or appropriate, prior to grading in order to ensure consistency and to exclude technical errors. Diurnal variations in laboratory variables and other measurements as well as baseline status and conditions will be taken into account when assessing whether abnormalities constitute a drug related AE and when grading, if applicable.

The CTCAE displays AE/toxicity Grades I through V with detailed clinical descriptions of severity for individual AEs based on a general guideline. The general grade definitions are described as follows:

Grade I: Mild; asymptomatic or mild symptoms; clinical or diagnostic observations only; intervention not indicated.

Grade II: Moderate; minimal, local or non-invasive intervention indicated; limiting age-appropriate instrumental Activities of Daily Living (ADL)\*.

Grade III: Severe or medically significant but not immediately life-threatening; hospitalisation or prolongation of hospitalisation indicated; disabling; limiting self-care ADL\*\*.

Grade IV: Life-threatening consequences; urgent intervention indicated.

Grade V: Death related to AE.

\*Instrumental ADL refer to preparing meals, shopping for groceries or clothes, using the telephone, managing money, etc.

\*\*Self-care ADL refer to bathing, dressing and undressing, feeding self, using the toilet, taking medications, and not bedridden.

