### 9.3 Exclusion criteria

Subjects will be excluded from enrolment in this study if they meet any of the following criteria:

1. Subjects with any medical history, conditions or risks, which, in the opinion of the investigator, may interfere with the subject's full participation in the study, or compliance with the protocol, or pose any additional risk for the subject or confounds the assessment of the subject or outcome of the study.
2. History of significant respiratory, renal, endocrinologic, hepatic, gastrointestinal, haematological, lymphatic, neurological, cardiovascular, psychiatric, musculoskeletal, genitourinary, immunological, dermatological or connective tissue disease or diseases,
3. History of malignancy,
4. History of relevant drug or other significant allergy,
5. Likely to need any treatment (including dental care) during the study period,
6. Significant infection or known inflammatory process at screening or Day -1,
7. Recent vaccination in the previous 2 weeks (from screening),
8. Donation or loss of more than 400 mL of blood within 90 days prior to the screening,
9. Use of any prescribed or over-the-counter medication within 14 days prior to first dosing (not including paracetamol in the range of 1g/day) or within 6 times the elimination half-life of the medication prior to first dosing (whichever is longest),
10. History or clinical evidence of alcohol or substance abuse. Alcohol abuse is defined as regular weekly intake of more than 21 units for males.
11. Confirmed positive results from urine drug screen (methamphetamine, opiates, cocaine, cannabis) or from the alcohol breath test at screening and on admission.
12. Current smokers (within 3 months prior to screening) and those who have a positive cotinine test,
13. Subjects who do not have suitable veins for multiple venipunctures/cannulation as assessed by the investigator at screening,
14. Supine blood pressure (BP) greater than 140/90 mmHg (systolic/diastolic) or less than 90/60 mmHg confirmed by at least 2 repeated measurements at screening and D-1,
15. Subjects who have clinically relevant ECG abnormalities (e.g. QTcB > 450 ms or notable sinus bradycardia with mean HR<40 bpm) confirmed by a repeat ECG at screening and D-1,
16. Family history of congenital long QT syndrome or known congenital arrhythmia,
17. Liver enzymes (ALAT, ASAT, ALP) exceeding the upper limit of normal range or 1.5 times the upper limit on D-1,

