**Spontaneously reported SAEs will be collected until 30 days following the final study visit.**

**SAEs experienced after this 30-day period will only be reported if the investigator suspects a causal relationship with the study drug.**

Adverse events (AEs) will be recorded in the CRF throughout the study from day of consent (screening visit) until the last follow up assessment.

Any AEs that are unresolved at the subject's last AE assessment in the study (i.e. at the end of study visit) are to be followed up by the Investigator for as long as medically indicated. INOTREM SA retains the right to request additional information for any subject with ongoing AE(s)/SAE(s) at the end of the study, if judged necessary.

Findings and values related to physical examinations and measurements of ECG, vital signs, (tympanic temperature, blood pressure, and heart rate) and laboratory parameters will be defined as AEs if they are considered clinically relevant deteriorations compared with screening values, as judged by the PI.

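### Section 12.3.1 calculates QTcF only once QTcB looks prolonged, so it can miss moderate QTcF prolongation at low heart rates, mainly at or below about 50 bpm

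*Combined protocol and SAP*

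**What the plan says.** Section 12.3.1 chooses the routine correction on grounds of convenience: "With regards to the clinical assessment of QTc interval, QTcB will be assessed as this is automatically calculated by the equipment". The Fridericia value follows only on a condition: "If there is any indication of potential significant QTcB prolongation, QTcF will also be calculated and assessed by a Research Physician". No number is attached to that condition, and further detail is left to the SOM. The same section requires at least 10 minutes of supine rest, recording in triplicate, and review of every ECG by a Research Physician.

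Nothing else in the documents makes QTcF routine. It appears otherwise only in the abbreviation list, and the ECG analysis in section 15.1.3 names no correction. The only QTc figure is an entry criterion, exclusion 15 in section 9.3: "clinically relevant ECG abnormalities (e.g. QTcB > 450 ms or notable sinus bradycardia with mean HR<40 bpm".

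Three later steps use the ECG reading:
- **AE definition (13.1.2).** ECG findings "will be defined as AEs if they are considered clinically relevant deteriorations compared with screening values, as judged by the PI".
- **Grading (8.3).** CTCAE "will be used to grade the AEs for the purpose of applying the toxicity rules".
- **Escalation (8.2.2).** Before each SRC meeting "an interim safety report will be prepared for that group/cohort presenting the relevant safety and tolerability data", and the required data include "ECGs variables (12-lead ECG, telemetry and Holter".

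**The concern.** The two corrections agree at 60 bpm and diverge on either side. Above 60 bpm QTcB is the higher value, so a conditional QTcF can clear a false alarm. Below 60 bpm QTcB is the lower value, and it also decides whether QTcF is calculated at all. The check therefore works in one direction only.

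Low rates are plausible here: healthy men aged 18 to 45, recorded after supine rest, with a mean rate below 40 bpm as the only bradycardia example in exclusion 15. Rates of 40 to 59 bpm are not ruled out by that example. The documents do not say how often they would occur.

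What is at stake is the reading of an individual ECG before the next dose level. Under section 8.2.4, escalation within Part B can rest on 24-hour data from three subjects on active drug, and Table 4 contains actions triggered by a single subject. At a low heart rate, the QTc routinely available for the judgement in section 13.1.2 is the lower of the two.

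**Working it through.** The plan gives no figure to reproduce. The inputs are the standard definitions of the two corrections and, as an **assumption**, a trigger of QTcB above 450 ms borrowed from exclusion 15. Section 12.3.1 itself states no trigger.

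**Step 1. Relation between the corrections.** With RR = 60/HR in seconds, QTcB = QT/RR^(1/2) and QTcF = QT/RR^(1/3). Dividing gives QTcF = QTcB × (60/HR)^(1/6).

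**Step 2. Highest QTcF that leaves QTcB at the trigger.** This is trigger × (60/HR)^(1/6). The 430 and 480 ms columns show the sensitivity to the assumption.

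| HR (bpm) | (60/HR)^(1/6) | Trigger 430 ms | Trigger 450 ms | Trigger 480 ms |
|---|---|---|---|---|
| 55 | 1.0146 | 436.3 | 456.6 | 487.0 |
| 50 | 1.0309 | 443.3 | 463.9 | 494.8 |
| 45 | 1.0491 | 451.1 | 472.1 | 503.6 |

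The width of the unflagged band hardly depends on the trigger: 6 to 7 ms at 55 bpm, 13 to 15 ms at 50 bpm and 21 to 24 ms at 45 bpm. At the 450 ms trigger it is about 1 ms at 59 bpm (451.3) and 31 ms at 40 bpm (481.5).

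**Step 3. Heart rate needed to miss a given QTcF at the 450 ms trigger.** Solving for HR gives HR ≤ 60/(QTcF/450)^6.
- QTcF 455 ms: 56.2 bpm or below
- QTcF 460 ms: 52.6 bpm or below
- QTcF 470 ms: 46.2 bpm or below
- QTcF 480 ms: 40.7 bpm or below

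So QTcF 460 ms at 55 bpm (QTcB 453.4) and 470 ms at 50 bpm (QTcB 455.9) both reach the trigger, while 460 ms at 50 bpm (QTcB 446.2) does not. QTcF 480 ms at 50 bpm gives QTcB 465.6 and is caught.

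**Step 4. If the judgement is on change from screening.** The factor is QTcB = QTcF × (HR/60)^(1/6), which is 0.9701 at 50 bpm.
- Constant 50 bpm, QTcF +30 ms: QTcB change = 30 × 0.9701 = +29.1 ms. Almost nothing is hidden.
- Rate falling from 60 to 50 bpm, QTcF 410 to 440 ms (+30 ms): QTcB goes from 410.0 to 440 × 0.9701 = 426.8, a change of +16.8 ms. Nearly half is hidden.

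**Step 5. Effect on summaries.** QTcF 400 ms at 50 bpm is QTcB 388.0 ms, 12 ms lower. One such subject among the 20 planned active subjects (2 in Part A, 18 in Part B) moves the active mean by 12/20 = 0.6 ms. Among the 18 in Part B the shift is 12/18 = 0.67 ms.

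**The case against.** The strongest reply is that the trigger is a physician's judgement with no cut-off. A reader may respond to a QTcB well under 450 ms or to a change from screening, and the SOM, which is not supplied, may say more. This stands: the 457, 464 and 472 ms figures are illustrations on an assumed trigger and do not describe a rule in the plan.

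Second, section 13.1.2 judges deterioration against screening values. Step 4 shows that at constant heart rate such a reading nearly closes the gap. This also stands. What is left for the change-based reading is the case where heart rate is lower on treatment than at screening.

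Third, every ECG is physician-reviewed and in triplicate, 12-lead telemetry runs from pre-dose to 10 h, and neither Table 4 nor Table 5 names a QTc value. These points limit the consequence. They do not put a QTcF in front of the reader when QTcB looks normal.

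A reader might infer that the check cannot reveal moderate prolongation at any rate below 60 bpm. Step 3 shows otherwise: close to 60 bpm almost nothing is hidden, and much moderate prolongation at 50 to 59 bpm would still reach a 450 ms trigger. A reader might also infer a bias in dose-group means seen by the SRC. The documents do not support that either. Section 15.1 summarises by IMP and time point, and on the SRC's view section 8.2.3 says "Initially the data will be reviewed blinded, but if the SRC consider it necessary due to a safety concern". The shift in the overall active mean is below 1 ms per affected subject (step 5).

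**Conclusion.** The concern holds in a limited form. Making QTcF conditional on QTcB leaves a band of moderate QTcF prolongation that can go unseen at low heart rates. On an assumed 450 ms trigger the band is about 7 ms wide at 55 bpm, 14 ms at 50 bpm and 22 ms at 45 bpm. A fall in heart rate from screening can also hide part of a true rise, as in the example of 16.8 ms shown for 30 ms. On the same assumption large prolongation is still caught.

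This rests on the standard Bazett and Fridericia definitions, on the assumed trigger, and on some subjects having rates near or below 50 bpm, for which the documents give no frequency. The documents do not show that any toxicity rule or escalation decision would come out differently. It is an optional, low-cost improvement of modest weight.

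**What to change.** In section 12.3.1, remove the condition on QTcF. Suggested wording:

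> QTcF will be derived for every recorded ECG from its QT and RR intervals and will be available with QTcB at the Research Physician's review. Both values will be shown in the interim safety report for the SRC.

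On any trigger, the band left unseen because QTcF was not calculated then becomes zero. No eligibility, stopping or other clinical threshold changes, and no ECG or subject is added.

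The cost is one derived variable and one more value to read per trace. Table 3 shows about eight ECG times per Part B subject, so three traces at each time in 24 planned subjects is 8 × 3 × 24 = 576 traces. On-study QT and RR must also be retained. QTcB already needs both, but section 12.3.1 states electronic storage expressly only for screening ECGs, so their retention is an inference and should be confirmed.

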### **12.3.2 Real Time Display (ECG Telemetry)**

A 12-lead real time ECG will be recorded as described in the Study Plan (Table 2 and Table 3). ECG telemetry will be monitored by the Investigator or qualified member of clinical staff. The system will be managed according to local working practices. The ECG telemetry reports will be archived with study documents.

### **12.3.3 24-hour Holter ECG**

Holter recording will be performed at screening as described in Table 2 and Table 3. If 12-lead holter recording is taken on screening, each electronic Holter ECG file will be downloaded onto the GE Gatemed Holter Analysis system. This will allow the extraction of ten-second 12-lead ECG data files, which can be transferred onto the MUSE. All ECG files so acquired will then be analysed and over-read using the same process as for any other 12-lead ECG.

## **12.4 Physical Examination, Height and Weight**

Physical examinations will be performed as detailed in the Study Plan (Table 2 and Table 3).

A full physical examination includes an assessment of the following: eyes, ears, nose, throat, cardiovascular, respiratory, musculoskeletal, venous system, gastro-intestinal, lymphatic, dermatological and neurological system.

A brief physical examination will be symptom oriented and will not include specific parameters of full physical examination.

Height will be measured in centimetres and weight in kilograms. Measurements should be taken with subjects wearing light clothing and without shoes using calibrated scales for all measurements. BMI will be calculated from the height and weight.

## **12.5 Pharmacokinetic Assessments**

For timing of individual samples refer to the Study Plan (Table 2 and Table 3). The date and time of collection will be recorded on the appropriate CRF.

### **12.5.1 PK Blood Samples**

Venous blood samples for the determination of concentrations of LR12 (active ingredient of MOTREM) in plasma will be taken at the times presented in the Study Plan (Table 2 and Table 3). For blood volume see Section [12.7](#).

All sample handling procedures, including the time of each sample collection, the time of placement into frozen storage (at the end of the sample workup), and the date of transfer or shipment of the samples to the responsible analyst will be documented in detail in the SOM. The procedures and materials used, e.g. collection and storage tubes, were examined prior to any analytical measurements as part of the analytical method validation, to rule out any possible interference with the analyte.

## 12.6 Immunogenicity

The presence of anti-LR12 antibodies will be assessed according to the Study Plan (Table 2 and Table 3). A blood sample will be collected for evaluation of potential immunogenicity evaluation from the appropriate vein for all healthy volunteers at the selected time-points. Sample analysis will be described in the SOM. Further details will be included in the SOM.

## 12.7 Volume of Blood Sampling

The total volume of blood that will be drawn from each subject in this study will be documented in the SOM and will not exceed 500 mL.

# 13 ADVERSE EVENTS

Safety will be determined by an evaluation of physical examination, vital signs, ECG parameters, laboratory tests and by the occurrence of AEs.

### Adverse event (AE)

Any untoward medical occurrence in a patient or clinical study subject administered a medicinal product and which does not necessarily have a causal relationship with this treatment. Events occurring prior to the first administration are part of baseline information.

An adverse event (AE) can therefore be any unfavourable and unintended sign (including an abnormal laboratory finding), symptom, or disease temporally associated with the use of an investigational medicinal product, whether or not considered related to the investigational medicinal product.

